The Thresholds Research Coordinator will schedule the study participants to complete 6 two-hour sessions of VR. When participants show up for the VR training, the visit will be run the Thresholds research staff who will provide the trainee with an initial orientation to VR and then monitor the trainee's access and performance scores during the sessions. After completing the initial 6 visits, trainees will move on to complete their post-test visit. Trainees will be invited to use VR as-needed after completing the post-test visit, which will be monitored by the Team Leaders. Those participants assigned to the SE as usual group will have the option to use the VR training in the context of their regular use of Thresholds services (i.e., they will not have access to the study resources to use VR) following the completion of their participation in the study (after their 9-month follow-up phone call). At each training session, any subject who has had to travel to use the intervention will receive \$10 to reimburse them for the cost of transportation.

A note on VR delivery procedures (1/29/18): When the study initially began, Employment Specialists and Team Leaders were asked to run the VR orientation and training sessions. Due to workload expectations and coordination barriers, this responsibility was moved to the Thresholds Research Team.

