# D. 6. Visit 10 (Post-test Visit completed at Northwestern University, at a Threshold's Odgen location, or via a phone call or video-conference) will be a repeat of the following measures (see D.2. and D.3. for more details):

- 1. Brief Psychiatric Rating Scale (BPRS)
- 2. Beck Depression Inventory (BDI)
  - a. Columbia-Suicide Severity Rating Scale (C-SSRS) if triggered by BDI scores
- 3. Job-Interview Role Plays
- 4. Social Skills Performance Assessment(SSPA)
- 5. Employment History Interview (follow-up version)
- 6. Job Interview Self-Efficacy
- 7. Personal Report of Job Interview Anxiety
- 8. Intrinsic Motivation Inventory
- 9. Technology Comfort Level Questionnaire is a 6-item measure that assesses one's comfort level with computer technology (approximately 5 minutes).

In addition, VR trainees will complete the 5 item Training Experience Questionnaire (TEQ; < 5 minutes). The

Posttest Visit 10 will last approximately 150 minutes or 2 hours and 30 minutes. Participants will be paid \$50.

**D. 7. Monthly Check-in Telephone Calls for Thresholds Clients (completed via telephone) will involve a brief (<10minutes) telephone survey asking about participants' potential interview or job-related activity in the past month.** These calls will be scheduled at monthly intervals after completion of post-test until the 6-Month Follow-Up (see D. 9.), for a total of 5 calls.

D. 8. Visit 11 (6-Month Follow-Up Visit completed at Northwestern University, a Threshold's Ogden location or via a phone call or video-conference) will be a repeat of the following measures (see D.2. and D.3. for more details):

- 1. Brief Psychiatric Rating Scale (BPRS)
- 2. AUDIT-SR
- 3. DAST-10
- 4. WHOQOL-BREF
- 5. SF-36
- 6. Beck Depression Inventory
  - a. Columbia-Suicide Severity Rating Scale (C-SSRS) if triggered by BDI scores
- 7. Employment History Interview (follow-up version)
- 8. Job Interview Self-Efficacy
- 9. Personal Report of Job Interview Anxiety
- 10. Intrinsic Motivation Inventory

Participants will also complete the SF-12 health questionnaire about their physical health and the Employment History Follow-up interview that will assess how many job interviews were completed, total hours worked, how many jobs were offered (and accepted), hourly wage, type of job, jobs terminated (and why).

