The 6-Month Follow-Up Visit 11 will last approximately 90 minutes or 1 hour and 30 minutes. Participants will be paid \$40. If the participant completed at least 3 of the 5 calls before the 6-Month Follow-Up visit, they will receive a \$10 bonus.

Follow-Up Visit 10 and Visit 11 scheduling protocol.

1. Study Participants' 6-month Follow-up visit (V11) will be scheduled 2-4 weeks before their due date. Scheduling will depend on the following:

a. If a participant is engaging in the monthly employment calls, their V11 will be scheduled at the time of their 5-month employment call.

b. If a participant is NOT engaging in the monthly employment calls, staff will contact the participant 4 weeks before the V11 due date. The contact process will be to use the phone to call the participant up to three times per week (only one time per day). Given that this population is difficult to reach, we will follow-up this initial phone call with an email and text message (for those participants who identified on their consent form that we can contact them by phone or emai.

2. If the study participant's V11 has not been scheduled by 2 weeks before their due date, staff will reach out to the participant's employment specialist and primary clinician for support contacting the participant.

3. If the study participant's V11 has not been scheduled by the time of their due date, staff will send a letter to the participant. The letter will explain the nature of the visit, the length of time the visit will take, and the staff person they should contact to schedule.

4. If the study participant does not respond to the letter or if their V11 is not scheduled by 6 weeks past their

due-date, staff will pull any available information from the electronic health record, and the member's study participation will end.

The same process will be used for scheduling Visit 10 as well.

Our primary method to collect Visit 10 and Visit 11 study data will be to invite participants to complete the visits at their local Thresholds location or Northwestern (as is the same for all in person study visits).

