### F. Participant Timelines

**F. 1. Thresholds Clients.** Individuals receiving mental health services at Thresholds who are enrolled in the effectiveness trial will participate in the study for a period of 9 months. Over the first month, they will complete a series of study measures and if randomized to the intervention group, this participation will include up to 10 hours of virtual reality training. After the first month, the participants randomized to the training group are

welcome to use the training as-needed, which will be monitored using their ID number. Then approximately 6 months after participants complete their post-test visit, they will be invited to complete their 6-month follow-up visit. Approximately 3 months after the 6-month visit, participants will be contacted via phone for a 9-month follow-up interview. Their participation in the study will end at this time.

After 1/3 of the effective trial participants have completed their intervention training (and before the completion of the 6 month follow-up) 20 VR trainees will be recruited to participate in a series of focus groups.

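### Read plainly, the rule that ends study participation also reaches Visit 10, so a client who cannot be scheduled for the post-test has no planned 6-month (T3) outcome collection

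*Combined protocol and SAP*

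**What the plan says.** Section 4.0 D.8 of the combined protocol and SAP sets out a four-step scheduling process. It moves from calls, email and text, to help from the employment specialist and primary clinician, to a letter. Step 4 opens: "If the study participant does not respond to the letter or if their V11 is not scheduled by 6 weeks past their" due date. At that point "staff will pull any available information from the electronic health record, and the member's study participation will end". The steps are written for Visit 11, the 6-month visit, but the block closes with "The same process will be used for scheduling Visit 10 as well", and no step is excepted.

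Two timing rules also depend on the post-test. For the monthly employment calls, D.7 says "These calls will be scheduled at monthly intervals after completion of post-test until the 6-Month Follow-Up". F.1 places the T3 visit about six "months after participants complete their post-test visit, they will be invited to complete their 6-month follow-up visit". The 9-month contact is timed from that visit.

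Section 14.0 calls the study intent-to-treat. H1 counts jobs obtained between T1 and T3, and its coding reads as giving 0 to clients with no job and to censored clients. H3 is time to employment by T3 and H4 is change in distress from T1 to T3. Multiple imputation is planned for longitudinal analyses, and the H1 power statement allows for 10% missing.

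**The concern.** Ending participation is a natural close when Visit 11, the last in-person visit, cannot be arranged. At Visit 10 the same step removes a client months before the main endpoints are due. Visit 10 contributes interim data, but the T3 endpoints for H1, H3 and H4 do not depend on it. A client who is unreachable around the post-test may well be reachable at month 6 or 7, and D.8 itself describes the population as hard to reach.

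Under the H1 coding, a client who leaves early and later finds work is counted as a failure, so the arm that loses more clients at Visit 10 looks worse. The loss could differ by arm. IPS+VR clients have six training visits first (D.5: "After completing the initial 6 visits, trainees will move on to complete their post-test visit"), while IPS Only clients have no scheduled study visit between pre-test and post-test. That the arms differ is an inference; the documents give no rate or direction.

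**Working it through.** **1. Is there another route to T3 for such a client?**
- Monthly calls: start after a completed post-test. None is planned otherwise.
- Visit 11: timed from a completed post-test. There is no due date otherwise.
- 9-month call: timed from the 6-month visit. There is no due date otherwise.
- Remote completion (D.8): needs a client who responds and agrees.
- Health-record pull: occurs at the cut-off and does not extend to T3. The documents do not say that the record holds BPRS or BDI scores.

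No section says that a client without Visit 10 stays in T3 follow-up.

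**2. Timing.** The post-test falls at about month 1 (F.1). Six weeks later is about month 2.5, and T3 is about month 1 + 6 = 7. About 7 − 2.5 = 4.5 months go unobserved. The unanswered-letter limb has no time limit of its own, so the cut-off could come sooner.

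**3. The plan's own H1 figure.** Inputs from 14.0: 80 per arm, 10% missing (80 × 0.9 = 72), control rate 25%, OR 3.2, two-sided alpha 0.0125. OR 3.2 implies (3.2/3)/(1 + 3.2/3) = 51.6%. A two-proportion test with 72 per arm gives 79.3% power, and a simulated Wald logistic test gives 79.8%. The stated 80% reproduces, but only after the whole 10% allowance is used.

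**4. Effect of losing clients at Visit 10.** The miss rates m are assumptions. The rest is the plan's 25% vs 53%, 80 per arm and alpha 0.0125.

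*All lost clients coded 0:* observed rate = p(1 − m).

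*Jobs before the cut-off captured:* observed rate = p(1 − m) + m·e, where e = 1 − (1 − p)^(2.5/7) under a constant hazard. This gives e = 9.8% for IPS Only and 23.6% for IPS+VR.

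Power = Φ(log OR / SE − 2.498), with SE² = 1/[80·a(1 − a)] + 1/[80·b(1 − b)] for observed rates a and b.

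| Lost, IPS Only / IPS+VR | Handling | Observed rates | Difference (points) | Power |
|---|---|---|---|---|
| 0 / 0 | complete | 25.0% vs 53.0% | 28.0 | 86% |
| 10% / 10% | coded 0 | 22.5% vs 47.7% | 25.2 | 78% |
| 5% / 15% | coded 0 | 23.8% vs 45.1% | 21.3 | 62% |
| 5% / 15% | early jobs captured | 24.2% vs 48.6% | 24.4 | 74% |
| 15% / 5% | coded 0 | 21.3% vs 50.4% | 29.1 | 89% |

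For the third row: log OR = 0.968, SE = 0.346, ratio 2.80, and Φ(2.80 − 2.498) = 0.62. For the fourth: a = 0.25 × 0.95 + 0.05 × 0.098 = 0.242, b = 0.53 × 0.85 + 0.15 × 0.236 = 0.486, log OR = 1.083, SE = 0.344, power 0.74.

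The last row shows that the reverse imbalance inflates the difference slightly (29.1 against 28.0 points).

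**The case against.** **The intent is not settled.** The sentence extending the process concerns scheduling, and step 1a cannot apply to Visit 10 as written, because "their V11 will be scheduled at the time of their 5-month employment call" refers to a call that takes place only after Visit 10. Section 10.0 names suicidality and symptom exacerbation as the anticipated grounds for withdrawal without consent; an unscheduled Visit 10 is not among them. F.1 gives participation as nine months. This stands as a reason for caution: that step 4 carries over is the plain reading, not a certain one. But even if it does not, D.7 and F.1 still leave the client without call dates or a T3 due date.

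**A reader might infer that missing one appointment removes a client.** The documents do not support that. The trigger is no response to the letter, or no visit scheduled by 6 weeks past due, after repeated outreach and with phone, video or teleconference offered.

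**A reader might infer that employment is never recorded for these clients.** The health-record pull may capture early jobs for H1 and H3. It cannot reach T3.

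**A reader might infer that Visit 10 serves only H2.** D.6 also lists the follow-up employment interview, BPRS and BDI, and the role-plays supply the H6 mediator. Losing Visit 10 therefore costs something in itself, but it does not make T3 uncollectable.

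**The analysis softens the loss.** The Cox model for H3 can censor these clients, and imputation is planned for longitudinal analyses. Neither replaces outcomes that could have been obtained, and the H1 coding turns early exit into failure.

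**The size can be overstated.** The plan's benchmark is 80% after 10% missing, so the symmetric 10% case (78%) is close to plan. The 62% combines an assumed imbalance with all jobs set to zero.

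**Conclusion.** The concern holds in a limited form. Followed as written, a randomised client who reaches the Visit 10 cut-off has no planned T3 collection. Employment data stop at whatever the health record holds at about month 2.5, and T3 distress is the clearest loss. This conflicts with the intent-to-treat aim and with D.11, which keeps clients who find work early in follow-up to month 6.

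The size is unknown, because the documents give no Visit 10 miss rate. Under the stated assumptions, H1 power moves from 86% with complete data to 78% with equal 10% loss. It moves to between 62% and 74% with 5% lost in IPS Only and 15% in IPS+VR. At those miss rates the falls are upper bounds on the rule's effect, because some of these clients would be lost at T3 under any rule. It would be wrong to read 62% as the trial's expected power, or to assume that the bias runs against IPS+VR; no documented rate supports either. The wording still needs correcting, because outcomes not sought at T3 may not be recoverable later.

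**What to change.** - **4.0 D.8, scheduling process:** limit the end of participation to Visit 11. State that a Visit 10 that is not completed makes only the Visit 10 measures missing.
- **D.7 and F.1:** when Visit 10 is not completed, time the monthly calls and the 6- and 9-month contacts from the Visit 10 due date, or from randomisation.
- **Coverage:** attempt Visit 11 for every randomised client who has not withdrawn or been withdrawn under the withdrawal rule in 10.0.
- **Section 14.0, a helpful addition:** say how employment information from the health record enters H1 and H3.

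The cost is short edits to three places, plus a few calls of under 10 minutes and one visit attempt for each affected client. No new assessment is needed.

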### F. Participant Timelines

**F. 1. Thresholds Clients.** Individuals receiving mental health services at Thresholds who are enrolled in the effectiveness trial will participate in the study for a period of 9 months. Over the first month, they will complete a series of study measures and if randomized to the intervention group, this participation will include up to 10 hours of virtual reality training. After the first month, the participants randomized to the training group are

welcome to use the training as-needed, which will be monitored using their ID number. Then approximately 6 months after participants complete their post-test visit, they will be invited to complete their 6-month follow-up visit. Approximately 3 months after the 6-month visit, participants will be contacted via phone for a 9-month follow-up interview. Their participation in the study will end at this time.

After 1/3 of the effective trial participants have completed their intervention training (and before the completion of the 6 month follow-up) 20 VR trainees will be recruited to participate in a series of focus groups.

### 5.0 Multiple sites:

This is a multi-site project funded by NIMH where the overall Principal Investigator is [name] located at University of Michigan with a subcontract to Thresholds to recruit participants, collect data, and provide the intervention, and a subcontract to NU to collect additional data as outlined in the procedures and manage all coordination activities of the study. After the study data is collected, entered, cleaned, and deidentified (except for video data) at Northwestern University, the electronic data will be shared with the overall PI on the project. [name] and his team at UM (his team is To Be Determined) will process and analyze the study data at UM.

The Northwestern PI ([name]) will be working closely with the Thresholds Site PI who is also the Research Director at Thresholds. In order to ensure successful coordination of research activities among sites, the Northwestern PI and Thresholds' Site PI will meet weekly and as-needed during the first 6 months of the study (and monthly and as-needed) to prepare and sustain a collaborative and agreed-upon approach. In addition, the Northwestern PI and Thresholds' Site PI will receive input from a community advisory board and an expert panel to review and discuss the approach for recruitment and data collection as well as to review and approve any modifications to the study protocol regarding recruitment or data collection methods. This panel will not have access to individual participant information or data. Recommendations to modify the protocol or consent form will be reviewed by the NU IRB and approvals will be immediately communicated via email to the Northwestern PI and Thresholds' Site PI, and both the NU and Thresholds' research coordinators as well as all project staff involved in the consent and data collection processes. As a safeguard, all IRB modifications will be reviewed at the next weekly research team meeting. All non-compliance with the research protocol will be reported to the Site PI and PI who will discuss and the PI will submit any deviations to the NU IRB for review.

## A signed IAA will be uploaded in the supporting documents in IRB modification #4 and before Thresholds staff engage in study activities with human subjects.

### 6.0 Incomplete Disclosure or Deception:

This study will not be using deception.

### 7.0 Recruitment:

**7.1** Research staff located at Thresholds ([name]) will sit in on weekly case coordination visits to educate Thresholds IPS staff about the study and discuss clients who may be a good fit for the study. The Employment Specialist will speak with the identified members to explain the study and see if they

are interested. The Employment or Research staff may also show the clients a **promotional video** about the Molly intervention to help them understand the study. If interested, the Thresholds research staff will reach out to the client directly via phone. The adults with SMI will complete a phone screener with the Thresholds Research Team to determine if they are eligibile for the study. If they are found eligible from the screener, the Research Team will schedule their first visit.

To recruit participants to evaluate the process of implementing VR within Thresholds, we will recruit the existing study participants using VR as well as Thresholds staff and leadership involved with the project. Each participant using VR, staff, and leader involved with the study will receive a study pamphlet summarizing the purpose of evaluating the implementation of VR. Individuals interested in completing this aspect of the study will be directed by the pamphlet to call the Research Coordinator at Thresholds to begin enrolling in this part of the study.

**7.2** The Thresholds Employment Specialist identifies members who are eligible for research participation base on member's enrollment and employment status. The Employment Specialist give members' information about the research study using the kickoff meeting recruitment script and kickoff meeting recruitment handout, and lets the member know that they may be eligible for the study. The Employment Specialist asks members if they would be interested in learning more about the study at a kickoff meeting with the research team. The kickoff meeting will be a two-hour period at a Thresholds location in which the interested member will have the option to talk to the Thresholds research team. The member will also have the option to talk to the Thresholds' research team via phone instead of attending the kickoff meeting. The Thresholds research team may use the Molly information video during the kickoff meeting. Once interest has been established in joining the study, the Thresholds research staff member will use the study screening form to determine the client's initial eligibility for the study participation, and then schedule a baseline visit. Screening data collected from the individuals who are ineligible or decline participation will be destroyed after recruitment is complete.

### 8.0 Consent Process

**A. Consent Location.** Participants with severe mental illness will be consented for the randomized controlled trial and their participation in the focus groups in a private research office located at the participants local Thresholds location (one of five locations: [name]; [name]; [name]; [name]; [name]). Participants with severe mental illness will be consented for their participation in the study during the initial consent process conducted at Thresholds. Thresholds staff and leadership will be consented at the above address on Ravenswood in either the research office or the staff or leader's own personal office.

**B.** Consent Team. The consent process taking place at Thresholds will be led by either the Study PI, Site PI, research coordinator, or research assistants who all have up-to-date CITI training.

**C. Consent Timeline.** The consent process will require approximately 10 minutes to read and up to 15 minutes to discuss to make sure that the participants fully understand the extent of their involvement in the study.

The details of the consent process including:

- i. Steps that will be taken to minimize the possibility of coercion or undue influence.
- ii. Steps that will be taken to ensure the participants' understanding.

**D. Consent Addendum for Visit 10 and 11.** For participants who are unable to attend Visit 10 and/or Visit 11 in person, we are providing these participants with the opportunity to complete abbreviated versions of the visit over the telephone or through videoconference (if available). In order to complete this process, the study team will call

the participants and read the consent addendum to them. When the participant provides their verbal consent (or not) then the study team will document the participant's decision and ID number on a hard copy of the addendum. Then the hard copy will be added to the participant's file. If the participant agrees to the consent addendum, then the study team will work with the participant to set up a time to complete the visit using the preferred method of communication.

